9.9.2 Analysis of Continuous Data Endpoints

The continuous data endpoints – the secondary endpoints of average decrease in resting SpO₂ from Baseline and average increase in resting pulse rate from Baseline during the 14 days of home follow-up or hospitalization – will be tabulated by mean changes on each post-treatment day from baseline and their 95% CIs by NasoVAX cohort, pooled placebo, and overall NasoVAX groups. The p-values from parametric (ie, Pearson's t-test) or nonparametric (ie, Mann-Whitney test) tests will be calculated to see significant differences in continuous endpoints between each NasoVAX cohort and pooled placebo groups and between overall NasoVAX and pooled placebo groups.

Changes from Baseline in Severity of COVID-19, assessed by average decrease in resting SpO₂, average increase in resting pulse rate by outpatient pulse oximetry and COVID-19 symptoms (eDiary) during home follow-up, will also be analyzed using mixed model for repeated measures (MMRM). The MMRM model will include the fixed effects of treatment, days, and treatment-by-visit interaction, and the stratification factors (ages 35-64 years vs. ages 65 years and above, one or more risk factors present vs. no risk factors present). The model will also include the baseline characteristics (gender, race) and the corresponding baseline measures (resting SpO₂ at Baseline, resting pulse rate at Baseline). The model will employ an unstructured within patient covariance matrix and a restricted maximum likelihood estimation method.

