### **10.3.2 Analysis of Efficacy**

For the primary analysis, the proportion of patients with clinical worsening, defined as a 4.0% decrease from Baseline in resting SpO2 on two successive measurements during home follow-up or hospitalization, will be compared between NasoVAX and placebo groups using the Cochran-Mantel-Haenszel test, while considering the stratification of age groups and risk factors, at a one-sided significance level of 0.025. The same approach will be applied for secondary endpoints that are categorical in nature. Sensitivity analyses will be performed to assess the effect of site on the response to study drug. Linear and logistic regression will be employed to examine the effects of Baseline factors, such as age, sex, medications, and medical co-morbidities on response.

Changes from Baseline in Severity of COVID-19, assessed by average decrease in resting SpO2, average increase in resting pulse rate by outpatient pulse oximetry and COVID-19 symptoms (eDiary) during home follow-up, will be analyzed using a mixed model for repeated measures. The model will include the fixed effects of treatment, week, and treatment-by-visit interaction as well as the continuous, covariate of Baseline level. The model will employ an unstructured within patient covariance matrix and a restricted maximum likelihood estimation method.

A Kaplan-Meier method will be applied to compare changes between treatment groups in resting SpO2 over time.

For the purpose of study efficacy endpoints, resting SpO2 and resting pulse rate will be assessed on observed data only; if data is missing, it will not be imputed.

No multiplicity adjustments will be made for secondary endpoints.

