4.2 Schedule of Events

The schedule for study activities is presented in [Table 2](#).

Confidential

Table 2 Schedule of Events – Screening and Treatment Periods

Procedure	Study Visit Type / Day			
	Screening	Study Drug Treatment	Diary Completion/ Telephone Contact	Telephone Contact
	Study Center Visit		Remote Visit	
	Day 1 Pre-Dose	Day 1	Daily Days 1 to 14	Days 21 and 28 ±2 days
Informed consent	X			
Eligibility criteria check	X			
Demographics	X			
Medical history	X			
Focused cardiovascular and respiratory physical examination	X			
Height and weight	X			
Blood pressure and respiratory rate	X			
Urine pregnancy test ^a	X			
Randomization	X			
Study drug administration ^b		X		
Resting SpO ₂ ^c	X		X ^d	
Resting pulse rate ^c	X		X ^d	
Oral temperature ^c	X		X ^d	
Baseline/Concomitant medications	X		X	X
AEs			X	X
eDiary completion for COVID-19 symptoms ^e	X		X	
Criteria for the Assessment of Severity of Illness in Patients with COVID-19 ^f	X			X
Daily telephone contact to document concomitant medications, clinical and hospitalization status and AEs ^g			X	
Follow-up contact for hospitalization status, COVID-19 outcomes, and AEs ^h				X

^a For women of child-bearing potential only. Results must be available and confirmed to be negative before study drug administration.

^b Study drug is to be administered with the patient in the supine position. The patient is to remain in the supine position for 30 minutes thereafter and be observed for at least 2 hours post intranasal administration.

^c To be measured remotely daily at 09:00 and 16:00 hours or at any time the patient experiences worsening symptoms using the study-supplied devices and recorded in the eDiary. Resting SpO₂ and pulse are to be measured at rest for 2 minutes. A ±1 hour window will be allowed. On Day 1, only the afternoon (16:00 hours) measurement is required and may be measured at the study center or remotely.

^d If the Screening visit occurs in the morning, the patient will be responsible for recording the 16:00 measurements at home later that day; if the visit occurs after 16:00, measurements will commence at home the following morning.

Confidential

- ^e The following symptoms will be recorded: fatigue, chills, headache, cough (with or without sputum production), myalgia, sore throat, shortness of breath, nasal congestion, diarrhea, and nausea or vomiting.

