Similarly, patients will be provided with a digital thermometer to measure oral temperature at 09:00 hours and 16:00 hours twice daily, with a 1-hour window around each time point, and at any time they experience worsening symptoms through Day 14, with results recorded in the eDiary.

Resting SpO₂ and resting pulse rate measurements will automatically be captured in the mobile device, while oral temperature will be captured in the eDiary ([Section 6.2.2](#)).

The Screening visit is defined as Day 1. If the visit occurs in the morning, the patient will be responsible for recording the 16:00-hour measurements at home later that day; if the visit occurs after 16:00 hours, measurements will commence at home the following morning.

6.2.2 eDiary

The eDiary will be completed by patient each day through Day 14. The following symptoms will be collected:

- Fatigue
- Chills
- Headache
- Cough (with or without sputum production)
- Myalgia
- Sore throat
- Shortness of breath
- Nasal congestion
- Diarrhea
- Nausea or vomiting

For each of these symptoms, the patient will be asked to grade them by the following scale:

- Not at all
- A little bit
- Somewhat
- Quite a bit
- Very much

The patient will also record all temperatures in the eDiary.

In the event that the patient progresses to hospitalization or is unable to complete the eDiary, family members, designated legal representatives or caregivers will be contacted, as provided by informed consent, to determine the status of the patient.

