7 ADVERSE EVENTS

7.1 Definitions

7.1.1 Adverse Event

An AE is defined as any untoward medical occurrence associated with the use of a drug in humans, whether or not considered drug related. An AE can therefore be any unfavorable and unintended sign (including an abnormal laboratory finding), symptom, or disease temporally associated with the use of the investigational product whether or not related to the investigational product. An AE can be any sign, symptom, or diagnosis that appears or changes in intensity during the course of the study.

Unchanged chronic conditions are not AEs and should not be recorded on the AE pages of the eCRF. These medical conditions should be adequately documented on the appropriate page of the eCRF (medical history or physical examination). However, medical conditions present on the first day of treatment that worsen in intensity or frequency during the treatment or post-treatment periods in a manner not consistent with natural disease progression should be reported and recorded as AEs. The Investigator will actively solicit this information and assess the event in terms of severity and relationship to the study treatment regimen.

The objective of this study is to assess the effective and safety of NasoVAX in preventing clinical worsening of early COVID-19. The worsening of fever, cough, shortness of breath, resting SpO₂ or resting pulse rate, and symptoms of COVID-19 that are reported in the eDiary during Screening will be captured in aggregate in the eCRF and will not be reported as AEs.

The term AE is used to include any AE whether serious or not serious.

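### The SAP's repeated-measures model for change in eDiary symptoms does not list baseline symptoms as a covariate, although they are collected at Screening; the cost is precision, not bias

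*SAP*

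**What the plan says.** SAP 9.9.2 takes change from Baseline as the response for three measures: resting SpO2, resting pulse rate and eDiary symptoms. For the last two it reads "resting pulse rate by outpatient pulse oximetry and COVID-19 symptoms (eDiary) during home follow-up, will also be analyzed using mixed model for repeated measures".

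The fixed effects are treatment, days, treatment by visit, and the two stratification factors. The text continues "The model will also include the baseline characteristics (gender, race" and adds "the corresponding baseline measures (resting SpO₂ at Baseline, resting pulse rate at Baseline". No symptom baseline appears in that list.

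Protocol 10.3.2 applies its model to the same three responses, but states the covariate generically: "as well as the continuous, covariate of Baseline level".

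A baseline symptom value exists. The schedule in SAP 4.2 has a row for "eDiary completion for COVID-19 symptoms" that is marked under Screening as well as Days 1 to 14. SAP 7.1.1 refers to "symptoms of COVID-19 that are reported in the eDiary during Screening". SAP 9.8 includes COVID-19 symptoms in the baseline summaries.

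The diary has ten symptoms with five verbal grades each (SAP 6.2.2): "For each of these symptoms, the patient will be asked to grade them by the following scale". The text available for review gives no numeric coding and no sum, mean or maximum to serve as the model's response.

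**The concern.** In a model of change from baseline, the baseline of the response is usually the most useful covariate. A patient who enters with a high symptom load has more room to fall than one who enters with a low load. If the baseline is not in the model, that variation stays in the residual and widens the interval for the treatment difference.

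Entry requires only one of fever, cough or shortness of breath (Protocol 5.2), so patients may enter with few or many of the ten diary symptoms. With 48 patients per arm, precision that costs nothing is worth having.

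The undefined score is a separate gap. Until a response is named, the analyst must choose between a sum, a mean, a maximum or single items, and that choice should be made before unblinding.

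**Working it through.** The documents give no power, effect size, SD or correlation for symptoms, so there is no stated figure to reproduce.

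**Inputs from the documents.** 10 + 14 + 24 = 48 patients per arm, 96 in total (SAP 4.1); change from Baseline as the response; SpO2 and pulse as the only listed baseline measures (SAP 9.9.2).

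**Assumed inputs.** Correlation ρ between the baseline and follow-up symptom score of 0.3, 0.5 or 0.7; baseline SD s0 and follow-up SD st equal unless stated; one post-baseline day with complete data.

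**Step 1. No other useful covariate.** Up to a common factor, the variance of the treatment contrast is:

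- change, own baseline omitted: s0² + st² − 2ρ·s0·st
- change, own baseline included: st²(1 − ρ²)

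The difference is (s0 − ρ·st)². It is never negative, so the direction does not depend on the assumed values. With equal SDs the ratio is 2(1 − ρ)/(1 − ρ²) = 2/(1 + ρ).

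| ρ | Variance ratio | SE ratio | Of 96 patients, effective number |
|---|---|---|---|
| 0.3 | 2/1.3 = 1.54 | 1.24 | 96/1.54 ≈ 62 |
| 0.5 | 2/1.5 = 1.33 | 1.15 | 96/1.33 ≈ 72 |
| 0.7 | 2/1.7 = 1.18 | 1.08 | 96/1.18 ≈ 82 |

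**Step 2. SpO2 and pulse already in the model.** If the listed covariates explain a share R² of baseline symptom variance, and predict follow-up symptoms only through it, the ratio is 1 + (1 − R²)(1 − ρ)/(1 + ρ). Suppose SpO2 and pulse each correlate 0.3 with baseline symptoms and are uncorrelated with each other. Then R² = 0.09 + 0.09 = 0.18:

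- ρ = 0.3: 1 + 0.82 × 0.7/1.3 = 1.44
- ρ = 0.5: 1 + 0.82 × 0.5/1.5 = 1.27
- ρ = 0.7: 1 + 0.82 × 0.3/1.7 = 1.14

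A simulation of 4,000 trials of 96 patients, with SpO2 and pulse in both models, gave 1.42, 1.28 and 1.13. With SpO2 and pulse unrelated to symptoms it gave 1.52, 1.31 and 1.18, in line with Step 1.

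**Step 3. Bias.** In the same simulations, with no true effect, the mean estimated difference lay between −0.001 and 0.007 baseline SDs, with or without the symptom baseline. That is noise around zero.

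**Step 4. Sensitivity to the SDs.** If the follow-up SD is half the baseline SD, the ratio is (1.25 − ρ)/[0.25(1 − ρ²)]:

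- ρ = 0.3: 0.95/0.2275 = 4.18
- ρ = 0.5: 0.75/0.1875 = 4.00
- ρ = 0.7: 0.55/0.1275 = 4.31

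In the other direction, the loss vanishes when ρ·st = s0. The size therefore cannot be fixed from the documents.

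**The case against.** The strongest reply is that baseline symptoms are already in the model. *Corresponding* most naturally means each response's own baseline. SAP 9.9.4 uses the same word with SpO2 or pulse for exactly those two endpoints, which suggests that the parenthesis in 9.9.2 names the two listed endpoints and simply overlooks the third response. SAP section 1 claims consistency with the protocol, whose generic Baseline level would cover symptoms. The precedence rule in SAP 9.13 applies only where there is a conflict, and an incomplete parenthesis may not be one. This reading is plausible and may be what was intended. It is still not what the list says, and a programmer who follows the list would leave the symptom baseline out.

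Second, little depends on this model. Symptoms are not among the endpoints in SAP 3.1 and 3.2, the study is exploratory and was not sized for significance, and SAP 9.10.2 gives symptoms their own tabulations and tests. This stands and keeps the point minor.

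Third, SAP section 11 (tables, figures and listings) is not in the text available for review and may define the symptom variable. The remark on the score is limited accordingly.

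A reader might also infer more than the documents support:

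- **That the treatment difference is biased by regression to the mean or baseline imbalance.** Under 1:1 randomization it is not. Chance imbalance in a single trial is part of the sampling variance computed above.
- **That the missing score causes the loss of precision.** It does not. The loss comes from the omitted covariate, and the score is a separate missing detail.
- **That the plan calls for ten item-level models.** SAP 9.9.2 does not say so; it leaves the response open.

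**Conclusion.** The point holds as a minor one. As listed, the symptom model in SAP 9.9.2 omits the baseline of its own response, although that value is collected at Screening and is needed to compute the change in the first place. The consequence is a wider interval for one supplementary comparison.

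With equal SDs and correlations of 0.3 to 0.7, the variance is 1.54 to 1.18 times that of the adjusted model if the listed covariates do not help, and about 1.42 to 1.13 times if SpO2 and pulse each correlate 0.3 with baseline symptoms. The correlations and SDs are assumptions, and the ratio is near 4 if the follow-up SD is half the baseline SD. Only the direction is firm. None of these figures should be quoted as the loss in this trial.

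The primary endpoint and the listed secondary endpoints do not depend on this model.

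**What to change.** In SAP 9.9.2, state that each repeated-measures model adjusts for the Screening (pre-dose) value of its own response: SpO2 for the SpO2 model, pulse rate for the pulse model, and the symptom score for the symptom model. This also brings the SAP back into line with Protocol 10.3.2.

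Before unblinding, name the symptom score, its numeric coding and a rule for missing items. A daily total of the ten items scored 0 to 4 (range 0 to 40) is one example; a mean or a maximum would also serve if fixed in advance. Single items can then be reported descriptively.

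The cost is a few lines of SAP text and one derived variable. No new data are needed. No patient is lost to the added covariate, because a change from Baseline already requires the Screening value.

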### 5.2 Inclusion Criteria

Patients who meet all of the following criteria are eligible for participation in the study.

1. Able and willing to provide informed consent

Patients themselves must provide written informed consent before the performance of any study-related procedures, and surrogate consent by family members, designated legal representatives, or caregivers will not be permitted.

2. Men and women 18 years of age and older

3. Early COVID-19, defined as one or more symptom(s) of fever (oral temperature  $\geq 100.4^{\circ}\text{F}$ ), cough or shortness of breath, onset of these symptoms within 72 hours of screening, and confirmation of SARS-CoV-2 infection by a PCR-based or rapid antigen test diagnostic

4. Resting  $\text{SpO}_2 \geq 96.0\%$  on room air on two successive measurements

5. For women of childbearing potential (women who are not permanently sterile [documented hysterectomy, bilateral tubal ligation, salpingectomy, or oophorectomy], postmenopausal [12 months with no menses without an alternative medical cause] or in monogamous same-sex relationships)

- Negative urine pregnancy test at Screening
- Willingness to practice a highly effective method of contraception that includes, but is not limited to, abstinence, sex only with persons of the same sex, monogamous relationship with a postmenopausal partner, monogamous relationship with vasectomized partner, vasectomy, licensed hormonal methods, intrauterine device, or consistent use of a barrier method (eg, condom, diaphragm) with spermicide for 28 days after the last dose of study drug

6. For men with sexual partners of childbearing potential, willingness to practice a highly effective method of contraception, as defined above, for 45 days after the last dose of study drug

---

7. Ability and willingness to comply with all aspects of the study, including reliable internet access, through the entire study period

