## **6.2 Randomization**

Following completion of the Screening activities, patients who meet all the inclusion and none of the exclusion criteria will be registered by the Interactive Web Response System (IWRS). Eligible patients will be randomly assigned in a 1:1 ratio to the NasoVAX or placebo group. Randomization will proceed in 3 cohorts defined by age and risk factors for severe COVID-19 ([Exclusion Criterion 5](#)) (Cohort 1, ages 18-49 years and risk factors disallowed; Cohort 2, ages 18 and above and risk factors disallowed; and Cohort 3, ages 18 and above and risk factors allowed) of approximately 20, 28, and 48 patients, respectively. The cohorts will be enrolled in ascending order, with Cohort 1 preceding Cohort 2, and Cohort 2 preceding Cohort 3. Cohort 2 will be stratified by age groups of 18-64 years and 65 years and above, whereas Cohort 3 will be stratified by age groups (ages 18-64 years, ages 65 and above) and co-morbidity (one or more risk factors present, no risk factors present). Patients in Cohorts 2 and 3 will be stratified first, and then randomized 1:1 to NasoVAX or placebo. Enrollment of patients ages 18-49 years will not exceed approximately 30% of the randomized population of either treatment arm. In addition, a minimum of 40% of Cohort 3 will either be 65 years or above or have one or more risk factors for severe COVID-19.

The randomization list will be generated by an independent unblinded statistician.

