### 10.3 Statistical Methods

#### 10.3.1 *General Methods*

Baseline is defined as data collected closest to randomization prior to any study drug dosing. For resting SpO2 and resting pulse rate, Baseline is defined as the average of the two measurements at Screening. All analyses and summary statistics will be presented by treatment group (NasoVAX, placebo) across cohorts, as well as by treatment group pooled across all cohorts, for each analysis set separately.

Descriptive statistics, including the numbers and percentages for categorical variables and the numbers, means, standard deviations, medians, minimums and maximums for continuous variables will be provided by treatment. The study is considered exploratory, and inferential statistics will be employed as appropriate across cohorts, as well as by treatment group pooled across all cohorts.

Patients will be randomized 1:1 to NasoVAX or placebo and proceed in 3 cohorts defined by age and risk factors ([Exclusion Criterion 5](#)) for severe COVID-19 (Cohort 1, ages 18-49 years and risk factors disallowed; Cohort 2, ages 18 and above and risk factors disallowed; and Cohort 3, ages 18 and above and risk factors allowed) of approximately 20, 28 and 48 patients, respectively. The cohorts will be enrolled in ascending order, with Cohort 1 preceding Cohort 2, and Cohort 2 preceding Cohort 3. Cohort 2 will be stratified

---

by age groups of 18-64 years and 65 years and above, whereas Cohort 3 will be stratified by age groups (ages 18-64 years, ages 65 and above) and co-morbidity (one or more risk factors present, no risk factors present). Patients in Cohorts 2 and 3 will be stratified first, and then randomized 1:1 to NasoVAX or placebo. Enrollment of patients ages 18-49 years will not exceed approximately 30% of the randomized population of either treatment arm. In addition, a minimum of 40% of Cohort 3 will either be 65 years or above or have one or more risk factors for severe COVID-19.

All descriptive and statistical analyses will be performed using SAS statistical software Version 9.2 or higher, unless otherwise noted.

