1 INTRODUCTION

This statistical analysis plan (SAP) is consistent with the statistical methods section of the final study protocol (Version 4.0, dated 28 July 2020) and includes additional details of efficacy and safety summaries to be included in the clinical study report (CSR).

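### The SAP codes the age stratum as 35-64 vs 65+, but the protocol enrols from 18 and stratifies at 18-64 vs 65+, so ages 18-34 have no level in the adjusted secondary models

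*SAP*

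**What the plan says.** **Protocol.** The age criterion in section 5.2 is "Men and women 18 years of age and older". Section 6.2 says "Cohort 2 will be stratified by age groups of 18-64 years and 65 years and above", and section 10.3.1 repeats this and adds "whereas Cohort 3 will be stratified by age groups (ages 18-64 years, ages 65 and above", crossed with co-morbidity. Cohort 1 (ages 18-49, no risk factors) is not stratified: "Patients in Cohorts 2 and 3 will be stratified first, and then randomized 1:1 to NasoVAX or placebo". Section 6.2 also limits the younger group: "Enrollment of patients ages 18-49 years will not exceed approximately 30% of the randomized population of either treatment arm".

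**SAP.** The MMRM in 9.9.2 includes the "stratification factors (ages 35-64 years vs. ages 65 years and above, one or more risk factors present vs. no risk factors present". The same age levels appear in:

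- 9.9.4 (ANCOVA at each post-baseline visit)
- 9.9.3 (optional time-to-event comparisons by stratum)
- 9.10 (safety comparisons by stratum)
- 4.1 and 4.4 (description of the randomisation strata)

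The cohort ages in 4.1 and Table 1, and the age cap in 4.1 and 4.4, also start at 35.

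The SAP does not present 35 as a planned change. Section 1 says that the SAP "is consistent with the statistical methods section of the final study protocol", and 4.3 sends the reader to Protocol 5.2 and 5.3 for eligibility. Section 9.13 says the SAP prevails where the two documents conflict.

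**The concern.** The two documents agree on the cut at 65 and disagree only on where the younger stratum begins. That matters because the SAP uses the stratum as a model term. A patient aged 18-34 is eligible, randomised and dosed, yet belongs to neither level of the factor as the SAP defines it. Mixed-model and ANCOVA software by default drops a record with a missing factor or covariate.

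Three things follow if the wording is coded literally:

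- The MMRM and ANCOVA for SpO2 and pulse rate would rest on fewer patients than the t-test or Mann-Whitney results that 9.9.2 plans for the same endpoints.
- The loss would fall only on the youngest patients. The comparison of NasoVAX Cohort 1 with pooled placebo would be the most exposed.
- Stratum comparisons under 9.9.3 and 9.10 would omit the same patients.

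The protocol text does not correct this by default. SAP 9.13 favours the SAP wording, and Protocol 10.4 lets the SAP supersede on analyses while protecting only the primary analysis.

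**Working it through.** The plan gives no figure to reproduce here: the sample size was not derived from power, and no age distribution is stated. The check is a comparison of text followed by bounds.

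**1. The age factor in each document**

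| | Younger level | Older level | Ages 18-34 |
|---|---|---|---|
| Protocol 6.2, 10.3.1 | 18-64 | 65+ | in the younger level |
| SAP 4.1, 4.4, 9.9.2, 9.9.3, 9.9.4, 9.10 | 35-64 | 65+ | no level |

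**2. Which analyses carry the bounds**

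- *Bounds stated:* MMRM, ANCOVA, optional time-to-event comparisons by stratum, safety comparisons by stratum.
- *No age bounds stated:* the primary CMH test, which Protocol 10.3.2 describes as "using the Cochran-Mantel-Haenszel test, while considering the stratification of age groups and risk factors", its counterpart in SAP 9.9.1, and the stratified log-rank test in SAP 9.9.3. No loss is claimed for these.
- *No stratum used:* Fisher's exact test, Clopper-Pearson intervals, t-test or Mann-Whitney, unstratified Kaplan-Meier. Not affected.

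**3. How many patients could lack a level**

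Inputs: cohorts of 20, 28 and 48, randomised 1:1 (Protocol 4.1), and the cap of about 30% per arm on ages 18-49 (Protocol 6.2).

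- Total: 20 + 28 + 48 = 96. Per arm: 10 + 14 + 24 = 48.
- Cap per arm: 0.30 x 48 = 14.4, about 14. Both arms: 2 x 14 = 28.
- Patients aged 18-34 are a subset of those aged 18-49, so their number lies between 0 and about 28. As a share: 28/96 = 29%.
- Fewest kept overall: 96 - 28 = 68.

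**4. The groups that SAP 9.9.4 compares**

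Cohort 1 is entirely aged 18-49 and uses 10 of the 14 places per arm. That leaves 14 - 10 = 4 per arm for ages 18-49 in Cohorts 2 and 3 together.

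| Group | Planned | Fewest kept under literal coding |
|---|---|---|
| NasoVAX Cohort 1 | 10 | 10 - 10 = 0 |
| NasoVAX Cohort 2 | 14 | 14 - 4 = 10 |
| NasoVAX Cohort 3 | 24 | 24 - 4 = 20 |
| NasoVAX overall | 48 | 48 - 14 = 34 |
| Pooled placebo | 48 | 48 - 14 = 34 |

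The minima for Cohorts 2 and 3 cannot both occur, because those cohorts share the 4 places. Jointly they keep at least 14 + 24 - 4 = 34.

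**5. Effect on precision (illustration only)**

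For a difference of two means with equal SDs and equal loss per arm, the standard error grows by sqrt(48/n), where n is the number kept per arm.

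| Patients lost in all | n per arm | Standard-error factor |
|---|---|---|
| 0 | 48 | 1.00 |
| 10 | 43 | 1.06 |
| 20 | 38 | 1.12 |
| 28 | 34 | 1.19 |

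**6. Other ways to code the factor**

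- A 65+ indicator (yes/no) gives every patient a level, so the loss is 0.
- The stratum held in the IWRS gives an age level to everyone in Cohorts 2 and 3. It gives none in Cohort 1, which is not stratified, and no risk-factor level in Cohort 2, which is stratified on age only.

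The SAP specifies neither.

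**The case against.** The strongest reply is that this is outdated text with little practical effect. The SAP cites protocol Version 4.0 of 28 July 2020, and other design details also differ from the protocol supplied: symptom onset within 48 rather than 72 hours, and up to 5 (SAP 4.3) or 6 (SAP 9.2) centres rather than 12. The SAP may have been written to different protocol text, in which case its reference to Protocol 5.2 says little about whether 35 was intended. A two-level factor split at 65 is also most naturally programmed as a 0/1 indicator, particularly in the ANCOVA, where only treatment arm goes in the CLASS statement. SAP 9.5 assigns the secondary analyses to an mITT set with no age limit, so dropping dosed patients would breach that definition. Finally, the bound of 28 uses the protocol's cap, while the SAP's own cap covers only ages 35-49.

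Part of this stands. An older protocol version is a plausible explanation, though the version of the supplied protocol cannot be seen. A sensible programmer may well lose no one, and the upper bound is not a forecast. But an explanation does not correct the text. The mITT definition conflicts with the literal factor and does not tell the programmer how to code it. The protocol's cap is the right one for the bound because enrolment follows the protocol.

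**Conclusion.** The concern holds. The SAP's age factor does not cover the population that the protocol enrols, and its precedence clause would keep the wrong wording. Under literal coding, between 0 and about 28 of 96 patients would have no level in the MMRM and ANCOVA, leaving as few as 68.

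The bound assumes planned numbers (the mITT set may be smaller) and enrolment under the protocol's cap. Its upper end needs that cap to be filled and every patient aged 18-49 to be under 35. The documents do not show where in the range the trial would fall.

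This should be corrected, but the stakes are limited: the affected models are secondary, the trial is exploratory, and no loss is claimed for the primary CMH test.

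**What to change.** Amend the SAP before database lock:

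1. Replace 35-64 with 18-64 in sections 4.1, 4.4, 9.9.2, 9.9.3, 9.9.4 and 9.10.
2. Align the cohort ages (4.1 and Table 1) and the age cap (4.1 and 4.4) with the protocol.
3. State that the strata in every stratified or adjusted analysis come from the IWRS record where it holds them. Assign Cohort 1 to the 18-64 level, and take risk-factor status in Cohorts 1 and 2 from Screening.

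The third item also settles the coding for the CMH and stratified log-rank tests, which name age groups without defining them. The cost is a wording amendment, with no new data.
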